This study will be conducted in accordance with the International Conference on Harmonisation guidelines for Good Clinical Practice (ICH E6), the Code of Federal Regulations on the Protection of Human Subjects (45 CFR Part 46), and Thomas Jefferson University research policies

List of Abbreviations

AE	Adverse Event/Adverse Experience
CEUS	Contrast-enhanced Ultrasound
CFR	Code of Federal Regulations
CIOMS	Council for International Organizations of Medical Sciences
CONSORT	Consolidated Standards of Reporting Trials
CR	Complete Response
CRF	Case Report Form
CRO	Clinical Research Organization
CT	Computed Tomography
CTCAE	Common Terminology Criteria for Adverse Events
DSMC	Data and Safety Monitoring Committee
DSMP	Data and Safety Monitoring Plan
ECOG	Eastern Cooperation Oncology Group
EMR	Electronic Medical Records
FDA	Food and Drug Administration
FWA	Federalwide Assurance
GCP	Good Clinical Practice
GWAS	Genome-Wide Association Studies
HCC	Hepatocellular Carcinoma
HI	Harmonic Imaging
HIPAA	Health Insurance Portability and Accountability Act
HVPG	Hepatic Venous Pressure Gradient
IB	Investigator's Brochure
ICC	Intrahepatic Cholangiocarcinoma
ICF	Informed Consent Form
ICH	International Conference on Harmonisation
IDE	Investigational Device Exemption
IND	Investigational New Drug Application
IRB	Institutional Review Board
ISPTA	Spatial-peak Temporal-average Intensity
LFT	Liver Function Test
MedDRA	Medical Dictionary for Regulatory Activities
MI	Mechanical Index
MOP	Manual of Procedures
MRI	Magnetic Resonance Imaging

mRECIST	Modified Response Evaluation Criteria in Solid Tumors
N	Number (typically refers to participants)
NCI	National Cancer Institute
NIH	National Institutes of Health
OHRP	Office for Human Research Protections
OLS	Ordinary Least Squares
PHI	Protected Health Information
PR	Partial Response
PI	Principal Investigator
PRC	Protocol Review Committee
QA	Quality Assurance
QC	Quality Control
ROI	Region of Interest
SAE	Serious Adverse Event/Serious Adverse Experience
SDS	Safety Data Sheet (formerly MSDS; Material Safety Data Sheet)
SHAPE	Subharmonic Aided Pressure Estimation
SKCC	Sidney Kimmel Cancer Center
SoC	Standard of Care
SOP	Standard Operating Procedure
SPECT	Single Photon Emission Computed Tomography
TARE	Transarterial Radioembolization
TACE	Transarterial Chemoembolization
TJU	Thomas Jefferson University
UAP	Unanticipated Problem
UCA	Ultrasound Contrast Agent
UTMD	Ultrasound-triggered microbubble destruction
Y-90	Yttrium-90

[figure not shown]
Study Summary

Title:	Contrast-Enhanced Ultrasound for Diagnosis and Therapy of Cholangiocarcinoma
Précis:	20 patients with biopsy-proven intrahepatic cholangiocarcinoma (ICC) or other non-HCC tumors in the liver will receive their standard of care (SoC) sub-lobar transarterial radioembolization (TARE), in addition to four sessions of ultrasound contrast infusion and ultrasound scanning. One session will be within 1 month prior to treatment and the other three will be at different time points after treatment. The treatment outcomes will be compared to a historical group of similar patients receiving TARE alone. The main hypotheses are that contrast-enhanced ultrasound (CEUS) can be used to predict non-HCC response to TARE prior to therapy, improve the sensitivity of these tumors to radiotherapy, and assess treatment response earlier than the current clinical standard.
Objectives:	To evaluate the utility of CEUS-derived quantitative measures in predicting tumor response before and in the early phases after TARE treatment, and to evaluate the safety and efficacy of microbubble cavitation in improving TARE treatment.
	Primary: 
• To determine the ability of quantitative volumetric CEUS to predict tumoral response to TARE prior to therapy.
	Secondary: 
• To characterize the safety and preliminary efficacy of using localized UCA inertial cavitation to improve non-HCC tumor response to radioembolization.• To determine if CEUS estimated tumor perfusion and residual vascularity can predict non-HCC tumor response to radioembolization 7-14 days post treatment.• To evaluate tumoral response using the patient's 1 month MRI (obtained clinically) and determine the accuracy of MR or CT tumor evaluation at this earlier time point.
	Exploratory: 
• To examine the utility of SHAPE to noninvasively monitor tumoral interstitial fluid pressure (IFP) and provide an early biomarker of radiotherapy response.
Population:	20 patients with intrahepatic cholangiocarcinoma (ICC) or other non-HCC tumors receiving sub-lobar transarterial radioembolization

(TARE). Patients at least 18 years of age, medically stable, and have a previously untreated tumor greater than 1 cm but small enough to be visualized in the ultrasound 3D volume will be included. These patients will be accrued from the Hepatology department, Interventional Radiology, and the Multidisciplinary Liver Tumor Board of the Sidney Kimmel Cancer Center at Thomas Jefferson University. All subjects must have read, signed, and dated the consent form(s) approved by the institutional review board of Thomas Jefferson University.

Phase:	Pilot
Number of Sites:	Thomas Jefferson University, Philadelphia, PA, USA
Description of Intervention:	Five ml of activated Optison will be suspended in 50 ml of saline and infused through an 18- to 22-gauge angiocatheter placed in an antecubital vein at a rate of 120 ml/hour (dosages based on prior approved Optison ultrasound-triggered microbubble destruction (UTMD) protocol and product insert) at the time points described above. All imaging will be performed using a modified Logiq E10 system with RAB6-D probe (GE Healthcare). For the second aim, a destructive (high mechanical index (MI)) pulse will be generated across the selected volume following peak enhancement (center frequency 2.1 MHz, pulse length 20 μ s, line density 4). Acoustic pressure amplitudes will be adjusted as necessary to ensure inertial microbubble cavitation.
Study Duration:	24 months
Participant Participation Duration:	3-6 weeks
Estimated Time to Complete Enrollment:	36 months

Schematic of Study Design:

1 Introduction

1.1 Background Information

Intrahepatic non-HCC tumors

A variety of both primary and metastatic cancers present in the liver. Cholangiocarcinoma is an aggressive epithelial tumor arising from the lining of the biliary tract with high morbidity and extremely poor prognosis. There are three tumor subtypes defined by the anatomical region from which they arise – intrahepatic, peri-hilar and distal (extrahepatic) bile ducts. Approximately 10% of cholangiocarcinomas are intrahepatic. Intrahepatic cholangiocarcinoma (ICC) is the second most common primary liver malignancy after hepatocellular carcinoma (HCC), accounting for 10-20% of primary liver tumors¹. Sadly, ICC incidence and mortality have been increasing in Western countries over the past two decades, highlighting the need to improve therapeutic options². Additionally, many non-liver cancers will first metastasize to the liver. These include (but are not limited to) uveal melanoma, neuroendocrine tumors, pancreatic cancers, breast cancer, and colorectal cancers. Management options for non-HCC tumors in the liver are limited and the disease generally portends a poor prognosis. Liver transplant is currently not an option and while curative surgical resection is the first line of therapy in patients with ICC without extension beyond the regional lymph nodes, it is only possible in less than 30% of cases with median disease free survival of 26 months^{1,3}. The majority of patients present with locally advanced or metastatic disease and are treated with systemic chemotherapy or loco-regional therapies. Liver-directed therapies including thermal ablation, transarterial chemoembolization (TACE), and transarterial radioembolization (TARE) are indicated for localized tumors^{4,5}.

Transarterial radioembolization

A meta-analysis of 12 studies in which 298 patients suffering ICC were treated with Yttrium-90 (Y-90) radioembolization reported overall median survival of 15.5 months⁶. TARE can be offered to patients with adequate performance status according to Eastern Cooperation Oncology Group (ECOG) performance score, blood cell count, liver function, and kidney function⁴. Additionally, TARE is being increasingly used for the treatment of other non-HCC solid tumors in the liver including colorectal cancer metastasis, uveal melanoma metastasis, and neuroendocrine metastasis. Using this approach, radioactive microspheres are delivered via a catheter placed in the hepatic artery branch supplying the tumor, thereby providing a localized and sustained release of radiation. The microspheres used are 20-30 μ m diameter glass beads containing Y-90. Y-90 is a pure beta emitter. It decays to stable Zirconium-90 with a half-life of 64 hours and has an average energy emission of 0.94 MeV. The maximum tissue penetration in the liver is 10 mm^{7,8,9}. Lobar doses range from 110-150 Gy, but radiation delivered to malignant tissue is dependent on distance from the yttrium source. Consequently, treatment response after radioembolization is between 25-60% when based on modified response criteria in solid tumors (mRECIST)^{9,6,10}.

Ultrasound contrast agents

Ultrasound contrast agents (UCA) are gas-filled microbubbles, encapsulated by a lipid or protein shell for stability. These agents are small enough (1-8 μm in diameter), to pass through the pulmonary capillaries, but are still restricted to the vascular system¹¹. These microbubbles have been approved for use in echocardiography and also for the characterization of liver lesions in the United States, Europe and Asia¹². UCA perfuse into the vasculature of liver tumors, and their wash-in/wash-out kinetics can be used to characterize liver masses (Figure 1). Both 2D and 4D CEUS can be acquired in hepatic tumors and used to quantify a variety of vascular parameters including blood flow dynamics and morphological features of the vasculature^{13,14}. Our group has demonstrated the exceptional safety and accuracy of contrast-enhanced ultrasound (CEUS) for monitoring response to chemoembolization of HCC¹⁵. Importantly, we have shown that the vascular networks of HCC depicted by CEUS can be used to predict the likelihood of a response to TACE¹⁴. We have also shown that UCA perfuse into liver tumors post TARE, due to the fact that the larger Y-90 beads (20-30 μm diameter) do not completely restrict blood flow. UCA can also be noninvasively destroyed in tissue using flash-replenishment sequences to generate inertial microbubble cavitation. Stable and inertial microbubble cavitation has demonstrated a variety of bioeffects useful for therapeutic applications¹⁶. Both stable and inertial cavitation have been shown to alter vascular and cellular permeability¹⁷.

Ultrasound-triggered microbubble destruction (UTMD) has also been shown to sensitize tumors to radiotherapy by inducing vascular endothelial cell apoptosis^{18,19,20}. This endothelial cell death has been attributed to increased ceramide production after interactions with inertially cavitating microbubbles²¹. Microbubble cavitation has also been shown to result in decreased tumor vascularity²². UTMD leads to increased DNA damage within the targeted tumor after radiotherapy, despite decreases in oxygenation²¹. Detailed parameter studies have been conducted in tumor xenografts, and synergistic combinations of UTMD and radiotherapy at mechanical indexes (MIs) > 0.8 , radiation dosages of 1.8-8 Gy, and microbubble concentrations of 1-3% (v/v) have been explored^{18,19}. Importantly, and yet somewhat paradoxically, UTMD in normal tissue increases vascular perfusion, due to cavitation-related increases in shear forces and activation of endothelial nitric oxide synthase²³. Hence, UTMD combined with radiotherapy potentially offers a tumor-specific method of tissue sensitization.

Optison

The proposed agent for the current study, Optison (GE Healthcare, Princeton NJ), is a sterile non-pyrogenic suspension of encapsulated perflutren microbubbles^{11,24}. The contrast agent consists of a human serum albumin shell with perflutren core and contains $5.0 - 8.0 \times 10^8$ microspheres/ml. The microbubble agent is supplied in a standard-size 3 ml vial and is prepared by manually shaking the vial. Optison is currently only approved for use in echocardiography. The agent will be used as an off-label indication for this study, but within the approved dosage recommendations.

Optison Clinical Safety

Optison is well tolerated and has been used extensively in echocardiography applications¹¹. In pre-market clinical trials, Optison was administered to 279 patients. In these patients 47 (16.8%) reported at least one adverse event. Of these events, 1 was classified as serious and required antihistamines for hypersensitivity manifestations of dizziness, nausea, flushing, and temperature elevation. No deaths were reported. Of the reported adverse reactions following the use of Optison the most frequently reported were headache (5.4%), nausea and/or vomiting (4.3%), warm sensation or flushing (3.6%), and dizziness (2.5%). Additional risks associated with the contrast material are described in the attached Optison Product insert (Appendix B). All of the non-serious reported side effects have been transient, usually lasting only a few minutes.

Table 1. Selected Adverse Events Reported in $\geq 0.5\%$ of the Subjects who Received Optison in Controlled Clinical Studies (From Optison Product Insert).

SELECTED ADVERSE EVENTS REPORTED IN $\geq 0.5\%$ OF THE SUBJECTS WHO RECEIVED OPTISON™ IN CONTROLLED CLINICAL STUDIES	
No. of Patients Exposed to OPTISON™	279
No. of Patients Reporting on Adverse Event	47 (16.8%)
Body as a Whole	38 (13.6%)
Headache	15 (5.4%)
Warm Sensation/Flushing	10 (3.6%)
Chills/fever	4 (1.4%)
Flu-like Symptoms	3 (1.1%)
Malaise/Weakness/Fatigue	3 (1.1%)
Cardiovascular System	12 (4.3%)
Dizziness	7 (2.5%)
Chest Pain	3 (1.1%)
Digestive System	12 (4.3%)
Nausea and/or Vomiting	12 (4.3%)

Nervous System	3 (1.1%)
Respiratory System	5 (1.8%)
Dyspnea	3 (1.1%)
Skin & Appendages	11 (3.9%)
Injection Site Discomfort	3 (1.1%)
Erythema	2 (0.7%)
Special Senses	9 (3.2%)
Altered Taste	5 (1.8%)
(1) Patients are counted separately within each body system. (2) The body system is reported if the aggregate is $\geq 0.5\%$. Details are not shown if the subsystem is not $\geq 0.5\%$.	

Additional information concerning pre-clinical and clinical experience with Optison, including the dosing levels and reported subject complaints, can be found in the Optison Package Insert that is included as Appendix B. As a tool, contrast-enhanced ultrasound is well documented for the characterization of indeterminate liver lesions including HCC and ICC, as well as the identification of a variety of solid tumor metastasis within the liver including breast, neuroendocrine, pancreatic, and colorectal cancers¹². Importantly, our group has also demonstrated the preliminary safety of using Optison with UTMD in patients undergoing Y-90 TARE of hepatocellular carcinoma²⁶.

Study goal

Our group has demonstrated the benefits of UTMD for sensitizing human HCC to radiotherapy in an orthotopic rat model²⁵. More recently, we have translated this work to a first-in-humans randomized controlled clinical trial using localized UCA cavitation with 2D ultrasound within HCC vasculature to sensitize liver tumors to radiation following radioembolization (NCT# 03199274). An example imaging series from this trial is shown in Figure 1. Our recent interim analysis of this trial²⁶ has demonstrated this approach is safe and results in promising radiosensitization. We intend to leverage our prior data in interventional oncology-based CEUS to improve treatment of ICC and other solid tumors within the liver. Consequently, the scientific premise of this work is that volumetric CEUS can be used to predict non-HCC tumoral response to TARE prior to therapy (thereby guiding selection of treatment option), improve the sensitivity of non-HCC tumors to radiotherapy (thereby improving tumor response), and assess treatment response earlier than the current clinical standard (thereby enabling earlier tumor retreatment when necessary).

[figure not shown]

Figure 1. Example series of a patient undergoing HCC radioembolization with UTMD. The series shows baseline MRI (A), Tc-99m MAA (macroaggregated albumin) SPECT-CT during treatment planning (B), angiography during Y90 delivery (C), B-mode ultrasound immediately post radioembolization (D), and peak CEUS enhancement during UTMD 2 hours (E), 1 week (F), and 2 weeks (G) post radioembolization [Eisenbrey et al. 2021].

1.2 Rationale for the Proposed Study

Contrast-enhanced Ultrasound

The sensitivity and specificity of ultrasound imaging can be improved by intravenous (IV) injection of gas microbubbles as vascular contrast agents, which can enhance both Doppler and grayscale signals by up to 27 dB^{27,11}. These contrast agents not only enhance the backscattered ultrasound signals, but at sufficient acoustic pressures they also act as nonlinear oscillators. These oscillations generate significant energy components in the received echo signals, which span the range of possible frequency emissions from subharmonics through ultraharmonics^{11,28}. These nonlinear bubble echoes can be separated from tissue echoes and used to create contrast sensitive imaging modalities such as harmonic imaging (HI), which is commercially available on most state-of-the-art ultrasound scanners^{27,11}.

CEUS is one of the most important advances in ultrasonography over the last two decades. One example is the rapid success in detection and characterization of focal liver lesions, where CEUS in many studies have demonstrated similar value as Computer Tomography (CT) and Magnetic Resonance Imaging (MRI)^{29,30,31}.

Safety of ultrasound contrast agents

Ultrasound contrast agents have minimal side effects compared to CT or MRI contrast agents. They are not toxic, and do not influence the metabolism of the thyroid gland. The most serious adverse event is anaphylactic reaction. The frequency of anaphylaxis using registered ultrasound contrast agents is very low (0.001 % for ultrasound contrast agents versus 0.07 % for X-ray contrast agents)^{32,33}. Contrast-enhanced ultrasound is well documented for the characterization of indeterminate liver lesions including HCC and ICC, as well as the identification of a variety of solid tumor metastasis within the liver including breast, neuroendocrine, pancreatic, and colorectal cancers¹².

Ultrasound-triggered microbubble destruction

Ultrasound-triggered microbubble destruction (UTMD) has also been shown to sensitize tumors to radiotherapy by inducing vascular endothelial cell apoptosis^{18,19,20}. This endothelial cell death has been attributed to increased ceramide production after interactions with inertially cavitating microbubbles²¹. Microbubble cavitation has also been shown to result in decreased tumor vascularity²². UTMD leads to increased DNA damage within the targeted tumor after radiotherapy, despite decreases in oxygenation²¹. Detailed parameter studies have been conducted in tumor xenografts, and synergistic combinations of UTMD and radiotherapy at MIs > 0.8, radiation dosages of 1.8-8 Gy, and microbubble concentrations of 1-3% (v/v) have been explored^{18,19}. Importantly, and yet somewhat paradoxically, UTMD in normal tissue increases vascular perfusion, due to cavitation-related increases in shear forces and activation of endothelial nitric oxide synthase²³. Hence, UTMD combined with radiotherapy potentially offers a tumor-specific method of tissue sensitization.

Subharmonic-aided pressure estimation

Ultrasound contrast agents were proposed as pressure sensors for noninvasive pressure estimation in the cardiovascular system using a novel and innovative technique called subharmonic-aided pressure estimation (SHAPE)³⁴. This method estimates internal pressure variations by transmitting at one frequency, receiving at its subharmonic frequency and then monitoring the subharmonic contrast bubble amplitude variations. We have demonstrated that the subharmonic signal component from contrast microbubbles is an excellent indicator of the hydrostatic pressure variation. High correlation ($r^2 > 0.95$) between the amplitude of the subharmonic component and hydrostatic pressure (from 0 to 186 mmHg) was obtained for several contrast agents *in vitro*³⁵.

We conducted a first-in-humans pilot study of this technique's ability to estimate portal pressures in 45 adult patients undergoing transjugular liver biopsy³⁶, which showed significantly higher SHAPE gradients between the portal and hepatic veins in subjects with clinically significant portal hypertension (HVPG > 10 mmHg) than in those with lower HVPGs (1.37 ± 0.59 dB vs. -1.68 ± 0.27 dB, $p < 0.001$). Recently, we have expanded on the concept of using SHAPE for portal pressure estimation in a larger multi-center trial³⁷. Results from 178 subjects across two sites

using modified GE Logic 9 systems (GE Healthcare) were very encouraging with an accuracy for diagnosing clinically significant portal hypertension of 95% (with a 95% confidence interval (CI): 89%-99%, $p<0.001$) and achieving a sensitivity of 91% (95% CI: 88%-93%) and a specificity of 82% (95% CI: 75%-85%). SHAPE offers the possibility of allowing pressure gradients in interstitial fluid pressure (IFP) in tumors to be obtained noninvasively^{36,38}. The role of tumoral IFP in radiation response remains relatively understudied due to difficulties obtaining these measurements with traditional wick-in-needle approaches³⁹. However, it has been proposed that tumor IFP drops following sufficient radiation exposure^{39,40,41}. We hypothesize that tumoral IFP estimated via SHAPE can be used as a biomarker to predict tumor response to TARE therapy.

1.3 Correlative Studies

Abdominal MRI/CT 3 months to two weeks before study inclusion and approximately 1-2 months and 3-6 months after treatment will be collected (as part of SoC). Post-treatment single-photon emission computed tomography (SPECT) imaging will be evaluated for all patients to evaluate if the initial UTMD session skews microsphere distribution in the liver. After the study period, the patients' records will be monitored until progression or death is documented. Each patient's time to required next treatment and overall survival will be recorded. The clinical outcomes and MRI/CT results will be used for evaluation of responses and local primary tumor progression.

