3.4 Duration of Follow Up

After the subjects have completed treatment, they will be followed through the electronic medical record (EMR) system for up to 1 year to document long term outcomes.

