6.4 Long Term/Survival Follow-up

After the subjects have completed treatment, they will be followed through the EMR system to for up to 1 year document long term outcomes.

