6.5 Withdrawal Visit/Discontinuation of Therapy

Patients who withdraw or are withdrawn from the study, will stop further CEUS procedures, as described by the study protocol. The reason for discontinuation shall be recorded. The investigators will follow any patient who develops significant adverse events.

Patients may be discontinued from study treatment and assessments at any time. Specific reasons for discontinuing a patient for this study are:

- Voluntary discontinuation by the patient who is at any time free to discontinue his/her participation in the study, without prejudice to further SoC treatment.
- Patient lost to follow-up.
- Safety reason as judged by the Principal Investigators.
- Severe non-compliance to protocol as judged by the Principal Investigators.
- Incorrect enrolment i.e., the patient does not meet the required inclusion/exclusion criteria for the study.
- Disease progression and/or rapidly deteriorating ECOG performance status.
- Deterioration in the patient's condition which in the opinion of the Principal Investigator warrants UTMD discontinuation (to be recorded as an AE or under Investigator Discretion)
 - Patient requires dialysis at any visit
 - Deteriorating liver function
- Related Serious Adverse Event
- A female patient becoming pregnant
- Any reason why, in the opinion of the investigator, the patient should not participate

The whole trial may be discontinued at the discretion of the PI or the sponsor in the event of any of the following:

- Occurrence of AEs unknown to date in respect of their nature, severity and duration
- Medical or ethical reasons affecting the continued performance of the trial

The sponsor and principal investigator will promptly inform all investigators and the relevant regulatory authorities of the termination of the trial along with the reasons for such action

7 Study Procedures and Evaluations

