11.1 Study Hypotheses

H1: Contrast reperfusion time, degree of tumor enhancement relative to the surrounding parenchyma, tumoral IFP and 3D morphological features of the vasculature quantified via CEUS before therapy correlate with SoC mRECIST reads of non-HCC tumor patients treated with TARE.

H2: mRECIST reads for non-HCC tumor patients receiving TARE combined with microbubble inertial cavitation have more complete response (CR) and partial response (PR) reads compared to the historical group treated with TARE alone.

H3: Patient's time to required next treatment and overall survival are longer for non-HCC tumor patients receiving TARE combined with microbubble inertial cavitation compared to the historical group treated with TARE alone.

H4: Observed and self-reported adverse events, and changes in liver function tests (LFTs) one month post-TARE in non-HCC tumor patients receiving TARE combined with microbubble inertial cavitation are similar compared to the historical group treated with TARE alone.

H5: Values of tumor perfusion and residual vascularity quantified by CEUS 2-4 hours, 1 week, and 2 weeks after TARE therapy are lower in CR and PR mRECIST reads of non-HCC tumor patients treated with TARE.

H6: Reductions of tumor perfusion and residual vascularity values quantified by CEUS 2-4 hours, 1 week, and 2 weeks after TARE therapy are more frequent in CR and PR mRECIST reads of non-HCC tumor patients treated with TARE.

H7: Tumoral response in mRECIST reads of MRI or CT (obtained clinically from patients treated with TARE) at 1 month post treatment will agree with response in their mRECIST reads at 3-6 months.

H8: Values of IFP quantified by SHAPE 2-4 hours, 1 week, and 2 weeks after TARE therapy are lower in CR and PR mRECIST reads of patients treated with TARE.

H9: Reductions of IFP values quantified by SHAPE 2-4 hours, 1 week, and 2 weeks after TARE therapy are more frequent in CR and PR mRECIST reads of patients treated with TARE.

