11.3.2 Efficacy Review

The primary measure of tumor response will be evaluated using mRECIST criteria as determined by [name] and [name] in consensus using 3-6 month contrast enhanced MRI or CT (blinded to patient group). Following a wait period and randomization of the patient order, both readers will also evaluate tumoral response using the patient’s 1 month MRI (obtained clinically) to determine the accuracy of MR or CT tumor evaluation at this earlier time point and its use as an alternative to CEUS. Finally, each patient’s time to required next treatment and overall survival will be monitored, although this is a secondary outcome for this study and expected to surpass the timeline of this study.

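### Section 1.3 ends record monitoring at progression, in conflict with 3.4, 6.4 and 11.3.2, and no censoring rule for H3 is given for either group

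*Combined protocol and SAP*

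**What the plan says.** Section 1.3 states that after the study period the patients' "records will be monitored until progression or death is documented". Its next sentence says that each patient's "time to required next treatment and overall survival will be recorded", without saying for how long.

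Section 3.4 has patients "followed through the electronic medical record (EMR) system for up to 1 year to document long term outcomes" once treatment is complete. Section 6.4 repeats this. Neither mentions progression.

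Section 11.3.2, in a sentence that also covers time to next treatment, says that "overall survival will be monitored, although this is a secondary outcome for this study and expected to surpass the timeline of this study". It gives no end date.

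Section 6.5 lists "Disease progression and/or rapidly deteriorating ECOG performance status" among the reasons for discontinuing a patient from study treatment and assessments.

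In Section 11.1, H3 states that time to next treatment and "overall survival are longer for non-HCC tumor patients receiving TARE combined with microbubble inertial cavitation" than in the historical group given TARE alone. Section 11.2 analyses H3 with Kaplan-Meier estimates and log-rank tests against 20 propensity-matched historical controls. It gives no censoring rule, no time origin and no follow-up rule for the controls.

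**The concern.** Kaplan-Meier and the log-rank test assume that patients censored at a given time have the same future risk as those still under observation. Progression breaks that assumption, because it marks a change in the risk of death and is a usual trigger for further treatment. If records are closed at progression, the later deaths and next treatments are never counted, and those patients leave the risk set just as their prognosis worsens.

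Two things are at stake. Within a group, the survival curve is too high. Between groups, the comparison depends on whether the stop falls on enrolled patients, on controls or on both, which the plan does not settle. With 20 patients per group, a rule chosen after outcomes are known would not be credible.

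**Working it through.** The plan gives no event count, hazard ratio (HR) or power for H3, so it has no figure of its own to reproduce here.

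**1. The follow-up statements side by side**

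| Section | End of follow-up | Stops at progression? |
|---|---|---|
| 1.3, first statement | progression or death, after the study period | yes |
| 1.3, next sentence | not given | not stated |
| 3.4 and 6.4 | up to 1 year after treatment is complete | no |
| 11.3.2 | beyond the study timeline | not stated |
| 11.2 (H3 analysis) | not given, for either group | not stated |

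The second sentence of 1.3 and Section 11.3.2 commit to recording the outcomes, but neither removes the stop.

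**2. Effect within one group**

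From the documents: median survival of 15.5 months (Section 1.1, intrahepatic cholangiocarcinoma). Assumed: median time to progression m of 5 to 9 months, and a hazard of death without progression h0 of 0.005 to 0.015 per month. The progression hazard is L = ln 2 / m. The hazard of death after progression, h1, is solved so that S(15.5) = 0.5, with

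S(t) = exp(-(L+h0)t) + [L/(L+h0-h1)] × [exp(-h1·t) - exp(-(L+h0)t)].

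- Survival at 12 months with full follow-up: S(12) = 0.61-0.62 across the range.
- Kaplan-Meier with censoring at progression sees only h0 and estimates exp(-12·h0). This is 0.94, 0.89 and 0.84 for h0 = 0.005, 0.010 and 0.015.
- Share of first-year deaths missed: 72-92%.

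One setting in full, with L = 0.12, h0 = 0.01, h1 = 0.08 per month (median survival 15.7 months):

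- S(12) = 0.210 + (0.12/0.05) × (0.383 - 0.210) = 0.62, or 7.5 deaths per 20.
- Deaths without progression: (0.01/0.13) × (1 - 0.210) = 0.061, or 1.2 per 20.
- About 84% of first-year deaths (1 - 1.2/7.5) follow progression and would be lost.
- With next treatment allowed only after progression (assumed 0.8 per month), next-treatment events fall from 12.6 per 20 to 0.

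**3. Effect between groups**

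Same hazards for controls, 200,000 simulated patients per group, 12-month horizon. Entries are overall-survival HRs, UTMD versus control.

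| True effect of UTMD | Both followed fully | Both stopped at progression | Only enrolled stopped | Only controls stopped |
|---|---|---|---|---|
| None | 1.00 | 0.99 | 0.29 | 3.37 |
| Halves progression only | 0.68 | 0.99 | 0.27 | 2.35 |
| Halves progression and death after it | 0.46 | 0.98 | 0.27 | 1.64 |
| Halves all three hazards | 0.36 | 0.50 | 0.14 | 1.26 |

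With both groups stopped, the HR is simply the ratio of the h0 values: 0.01/0.01 = 1 in the first three rows and 0.005/0.01 = 0.5 in the last, up to simulation error. Any effect on progression, or on death after it, is invisible. The attenuation is therefore a feature of these scenarios. An effect confined to deaths before progression would be exaggerated instead.

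**4. What a common 12-month rule would yield**

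With exponential survival and a median of 15.5 months in both groups, deaths among 40 patients are 40 × (1 - 2^(-12/15.5)) = 16.6. For assumed medians of 24 and 10 months they are 11.7 and 22.6. Log-rank power at an assumed HR of 0.5 is Φ(½·√16.6·ln 2 - 1.96) = 29% (22% to 38% over that range).

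**The case against.** The strongest reply is that one sentence in a background section is being read literally against the rest of the protocol. The sentence applies only after the study period, which is not defined; the Study Summary gives 3-6 weeks of participation and a 24-month study. If that period includes the year of record review, the rules run in sequence and 12-month survival is not cut. The next sentence of 1.3 promises both outcomes for every patient, 3.4 and 6.4 contain no progression stop, and 11.2 does not ask for censoring at progression. This stands as an argument that the damaging reading is not the only one. It does not settle the matter, because no section says which rule governs H3.

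A reader might go further and infer that the 1.3 stop biases H3 in favour of UTMD. The documents do not support that. It requires enrolled patients to be cut at progression while controls are followed to death, and nothing says that controls have fuller records. Section 11.2 says only that they are recently treated patients at the same institution, and enrolled patients are themselves followed through the electronic record. The table above shows the direction reversing with the assumption.

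Two limits of the illustration also stand. The progression and death hazards are assumptions, including the premise that most deaths follow progression. The 15.5-month median is for intrahepatic cholangiocarcinoma, while the trial also enrols other non-HCC tumors.

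**Conclusion.** The point holds as a conflict between stated follow-up rules, one of which would give a wrong result for H3 if followed, together with a missing censoring rule for both groups. Applied literally, the 1.3 stop would inflate 12-month Kaplan-Meier survival to about 0.84-0.94 from 0.61-0.62 and lose most first-year deaths. Those sizes are single-group and illustrative. They rest on the assumed hazards and cannot be read as a treatment difference.

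The between-group effect is undetermined by the plan. Under no true effect, the HR in the simulation was 0.29, 3.37 or 0.99 according to whether enrolled patients only, controls only or both were stopped.

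The weight is moderate. H3 concerns secondary outcomes in a 20-patient pilot with no stated time-to-event power, and even complete 12-month follow-up would leave the log-rank test weak. The change is worth making because it costs little and has to be settled before outcomes are examined.

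**What to change.** Remove the progression stop from Section 1.3 for these two outcomes, and state one rule consistently in 1.3, 3.4, 6.4, 11.2 and 11.3.2:

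- Follow every enrolled patient through the electronic record for next treatment and death, regardless of progression, to one common cut-off measured from TARE. The cut-off should be at least the 1 year already planned. If the longer monitoring foreseen in 11.3.2 is wanted, name its end date.
- Apply the same time origin, length of follow-up and censoring to the matched historical controls.
- State in 11.2 how patients alive or lost at the cut-off are censored, and how death before a next treatment is handled in the time-to-next-treatment analysis.

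This concerns record follow-up only and leaves the discontinuation reasons in Section 6.5 as they are. The cost is a few sentences in a protocol amendment and some additional chart review, with no extra visits.
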